6.5.7 Subgroup Analyses

The specification of subgroup analyses is the same as described in the M-SAP with the following modifications. Analyses will use the ECC analysis set focusing on comparisons between ABBV-CLS-7262 120 mg vs. placebo at 24-week change from baseline. Early disease state is defined as all ALSFRS-R questions scored 2 or greater, SVC 80%-predicted or greater, time since symptom onset less than 24 months, and El Escorial definite or probable. Baseline CSF GDF-15 concentration (median split), baseline CSF FGF21 concentration (median split), and baseline serum NfL concentration (median split) are added as additional subgroup analyses to explore treatment efficacy of ABBV-CLS-7262 in different subgroup populations. Body mass index (BMI), baseline symptom severity defined by ALSFRS-R questions scored 2 or greater, baseline plasma NfL, and site are removed as subgroups.

6.5.8 Comparison of Controls across Regimens

The specification of comparisons of controls across regimens is the same as described in the M-SAP with the addition that comparisons will be made across regimens in both the FAS and ECC analysis sets.

6.5.9 Pharmacodynamic Biomarker Analyses

Change in pharmacodynamic biomarkers will be summarized by treatment group and visit in the ERO analysis set. Summary statistics will include number of observations, number and percentage with concentrations BLQ, arithmetic mean, median, standard deviation, minimum, maximum, geometric mean, geometric coefficient of variation (calculated as sqrt(exp(variance of log-transformed concentrations) – 1)), and 95% confidence bounds for the geometric mean assuming log-normally distributed data. Summaries will include observed values, absolute change from baseline, and percent change from baseline at each scheduled assessment time point.

The effect of treatment on pharmacodynamic biomarker response will be estimated in the repeated-measure model (see Section 6.5.2). Pearson and Spearman correlations between change in levels of pharmacodynamic biomarkers and concurrent change in ALSFRS-R total scores and SVC percent-predicted will be estimated at each visit among participants with complete data.

6.6 Safety Analyses

6.6.1 Treatment-emergent Adverse Events

Summaries of treatment-emergent adverse events (TEAEs) are the same as described in the M-SAP with the addition of the SCC analysis set and the addition of summaries of abuse-related TEAEs (see Appendix 2 Monitoring Abuse Potential of ABBV-CLS-7262 in Clinical Trials, Ad-Hoc Statistical Reporting Plan, Version 1.0 – June 28, 2023).

6.6.2 Safety Labs

Summaries of safety labs are the same as described in the M-SAP with the addition of the SCC analysis set and the addition of summaries for assays specific to RGF: amylase, lipase, ACTH, cortisol, total testosterone (males only), luteinizing hormone (males only), TSH, free T4, T3, and abnormal cosyntropin stimulation response.

6.6.3 ECG Results

Summaries of ECG results are the same as described in the M-SAP with the addition of the SCC analysis set and shift tables for abnormal findings.

6.6.4 Vital Signs and Weight

Summaries of vital signs are the same as described in the M-SAP with the addition of the SCC analysis set. Weight will be analyzed in the FAS, ECC, and ERO analysis sets in the repeated-measures and random-slope mixed models.

6.6.5 Suicidality

Summaries of suicidality are the same as described in the M-SAP with the addition of the SCC analysis set.

6.7 Other Analyses

6.7.1 Participant Disposition

Summaries of participant disposition are the same as described in the M-SAP.

6.7.2 Study Drug Compliance and Tolerance

Summaries of study drug exposure and tolerance are the same as described in the M-SAP. The proportion of participants who are compliant with study drug as defined in Section 5.12 will be summarized for participants in the ABBV-CLS-7262 120 mg and 240 mg treatment groups. Drug accountability discrepancies will be listed according to Appendix 2.

6.7.3 Concomitant Medication Use

Summaries of concomitant medication use are the same as described in the M-SAP with the clarification that use at baseline refers to use of a concomitant medication at the time of first dose of study drug, and that initiation after first dose of study drug is defined as first use of a concomitant medication after first dose of study drug that was not being taken at the time of first dose of study drug.

6.7.4 Medical History

Summaries of medical histories are the same as described in the M-SAP with the addition of a summary for the SCC analysis set.

6.7.5 Blindedness

Summaries of blindedness are the same as described in the M-SAP with the addition of a summary for the ECC analysis set.

6.7.6 Protocol Deviations

Summaries of protocol deviations are the same as described in the M-SAP.

7. Validation

7.1 Primary Efficacy Analysis

Validation of the primary efficacy analysis is the same as described in the M-SAP.

1.0 Introduction

This document describes the primary endpoint, primary analysis, and interim analyses for Regimen F (ABBV-CLS-7262).

Regimen F follows the recommended design, primary endpoint and primary analysis from the ALS Master Protocol Recommended Statistical Analysis, Design and Simulation Report Dated February 6, 2023 (Appendix I of the HEALEY ALS Platform Trial Master Statistical Analysis Plan v3.0) with 2 minor differences:

- 1) Inclusion of two doses (120 and 240 mg QD) with primary inference being focused on the 120 mg QD dose, referred to as the anchor dose. Interims for futility will require both doses to meet the requirement for futility (Section 2.1 and 2.3).
- 2) The primary analysis population includes all participants in the Full Analysis Set who were randomized within Regimen F or randomized to placebo within Regimen G, exclusive of Regimen G participants who previously randomized within Regimen F (Section 2.1).

The design for Regimen F enrolls approximately 300 participants. Approximately 165 participants will be randomized to ABBV-CLS-7262 120 mg, approximately 60 participants will be randomized to ABBV-CLS-7262 240 mg, and approximately 75 participants will be randomized to placebo.

This document serves to provide:

- Modifications to the primary analysis model to include a treatment effect for both doses of ABBV-CLS-7262, details of primary success criteria for the anchor dose, and details of futility criteria including both doses.
- A list of sensitivity analyses that will be performed.
- Simulations custom to Regimen F that include 300 participants enrolled to both doses within Regimen F and concurrent shared controls from Regime G.

2.0 Overview of Primary Analysis and Design

2.1 Primary Analysis

The primary analysis population includes the subset of participants in the Full Analysis Set who were randomized within Regimen F or randomized to placebo within Regimen G, exclusive of Regimen G participants who previously randomized within Regimen F (Efficacy Concurrent Controls analysis set).

The primary analysis is a Bayesian shared parameter analysis of mortality and function (ALSFRS-R) and is described in the ALS Master Protocol Recommended Statistical Analysis, Design and Simulation Report Section 2.0 Dated February 6, 2023 (Appendix I of the HEALEY ALS Platform Trial Master Statistical Analysis Plan v3.0). For Regimen F, the model will be modified to include independent treatment effects for each dosage of ABBV-CLS-7262.

The treatment effect for T=0,1,2 (control, anchor, and high dose respectively) is parameterized as the disease rate ratio (DRR): $\exp(\theta_T)$. For a placebo patient, the DRR is set equal to 1 (θ_0 = 0). The prior distribution for the DRR for the anchor dose and high dose in Regimen ABBV-CLS-7262, T=1,2, is uniform between 0 and 2, placing equal weight on a DRR<1 and DRR>1:

$$\exp(\theta_T) \sim Unif(0,2), T = 1,2.$$

The primary analysis will compare the anchor dose to control. The comparison of the high dose to control will be a secondary analysis.

2.2 Regimen Success

The primary analysis in Regimen F will test the anchor dose, T=1, compared to placebo. Success will be declared for the anchor dose at the final analysis if the posterior probability that the dose is superior to placebo group is greater than .975:

$$Pr(\exp(\theta_1) < 1) > .975.$$
; for anchor dose

The threshold for the final analysis of .975 was chosen to control type I error at 2.5% in the null scenario without futility stopping.

2.3 Interim Analyses and Regimen Futility

Interim analyses occur simultaneously for all regimens within the platform that have participants active in their placebo-controlled period. Interim analyses occur

approximately every 12 weeks. The first interim analysis for Regimen F will be performed after there are 60 randomized participants within Regimen F who have had the opportunity to complete at least 24 weeks of follow-up. At an interim analysis, Regimen F can stop early only for futility. If Regimen F is not stopped early for futility at an interim analysis, then the Regimen F final analysis will take place after all participants randomized within Regimen F have had the opportunity to complete 24 weeks of follow-up and final data for the Regimen F placebo-controlled period have been locked.

The primary analysis population for early interims on futility will include the subset of participants in the Full Analysis Set who were randomized within Regimen F or randomized to placebo within Regimen G, exclusive of Regimen G participants who previously randomized within Regimen F.

For interim analyses, due to constraints on when serum NfL data is received, the covariate of baseline log-transformed serum NfL level will not be included in the primary analysis model.

Futility will be declared for Regimen F at an interim analysis if the posterior probabilities that the anchor dose, T=1, and the high dose, T=2, slow disease progression by at least 10% are both less than 5%:

$$Pr(exp(\theta_1) < .9) < .05 \text{ and } Pr(exp(\theta_2) < .9) < .05$$

2.4 Goodness of Fit Diagnostics and Sensitivity Analyses of Primary Efficacy Analysis

The goodness-of-fit diagnostics, supportive analyses, and sensitivity analyses will be performed for the primary efficacy analysis and will be conducted on the primary analysis population unless otherwise specified. Analyses will follow those specified in Section 4.0 of the ALS Master Protocol Recommended Statistical Analysis, Design and Simulation Report Dated February 6, 2023 (Appendix I of the HEALEY ALS Platform Trial Master Statistical Analysis Plan v3.0) with the following modifications:

 Concurrent shared control population will serve as the primary analysis population and a sensitivity analysis with all shared controls from Regimens A-G will be conducted.

3.0 Clinical Trial Simulations

Clinical trial simulation is used to provided simulated example trials and to quantify operating characteristics for each regimen. Virtual patient outcomes are created under different assumptions for key design parameters (see ALS Master Protocol Recommended Statistical Analysis, Design and Simulation Report Section 5.1 Dated February 6, 2023 [Appendix I of the HEALEY ALS Platform Trial Master Statistical Analysis Plan v3.0] for description of simulation method). For each set of simulation assumptions (i.e., a scenario), many trials are simulated and virtually executed, including all interim analyses for early futility. Trial operating characteristics are summarized across all simulated trials for each scenario.

3.1 Simulation Scenarios

Trial simulations for Regimen F assume that Regimen F is the 6th regimen with a 7th regimen (Regimen G) also enrolling concurrently with a total of N=240 and 60 controls in Regimen G. Under the primary concurrent only shared control analysis there is expected to be a total of N=165 treated on the anchor 120mg dose in Regimen F and N=135 shared controls. Treatment effect assumptions will vary across the anchor dose for Regimen F and operating characteristics will be reported for this regimen/dose. The other 6 regimens will be assumed to be Null (no benefit on ALSFRS-R or mortality).

Additional simulation assumptions are:

- Accrual of 40 participants per month
- · Non-mortality dropout rate of 2% per month
- · Mortality rate of 5% over 24 weeks.
- ALSFRS-R slope distribution and measurement error for Regimen F is the same as PRO-ACT
- Rates of usage and effects of Standard of care (SOC). Effects of SOC will be multiplicative effects to the individual rates of progression applied first before any treatment effect (see below).
 - Edaravone usage at baseline is 25% with an assumed 30% slowing over natural progression for those participants who are on edaravone
 - Relyvrio usage at baseline is 60% with an assumed 25% slowing over natural progression for those participants who are on Relyvrio
 - $\circ~$ The treatment effect for those participants on both edaravone and Relyvrio is capped at 30% slowing.

Treatment effects for Regimen F will be simulated under the Null with 0% slowing in disease progression and under an alternative with 30% slowing in disease progression. The 30% slowing due to treatment in Regimen F is assumed to be an additional, additive effect on top of any effect of the standard of care (see SOC effect above). This additive effect on the slope will be specific to each SOC group (those not on edaravone or Relyvrio, those only on edaravone, those only on Relyvrio, and those on both) based on the expected control rate of progression within that subgroup to achieve a 30% slowing.

Simulations are performed without futility stopping.

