9.3 Regimen Specific Operating Characteristics

Clinical trial simulations customized for Regimen F (ABBV-CLS-7262) are provided in Appendix I to the R-SAP. The primary comparison of the anchor dose (120 mg) to placebo control is powered at approximately 80% to detect a 30% slowing in disease progression (common to mortality and function decline). The type I error of the regimen is 2.5% assuming no systematic differences in rates of progression across regimens contributing to the concurrent controls. More details are provided in Appendix I to the R-SAP.

[figure not shown]
Given the sample size of 165 participants on 120 mg (RCT treatment)/120 mg (ATE treatment) and 75 participants on placebo (RCT treatment)/120 mg (ATE treatment), the study will also have approximately 85% power on the CAFS at ATE Week 52, and approximately 80% power for survival through to the end of the ATE period. Such calculations were performed with assumptions for an 18-month survival rate of 70% for placebo RCT/120 mg ATE group and an 86% survival rate for 120 mg RCT /120 mg ATE group at ATE Week 52, with a 12-month accrual period (totaling a maximum study duration of 30 months) and 13% drop-out rate due to non-mortality reasons. The treatment difference for change from baseline in ALSFRS-R total score was assumed 20% slowing of disease progression rate versus delayed initiation of ABBV-CLS-7262 with a standard deviation of 9.0 at ATE Week 52 (accounting for a partial cross-over effect). An exponential distribution was assumed for power assessment of CAFS and survival endpoints. These tests for power analysis were done with a two-sided significance level of 0.05.

[figure not shown]

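### The control mortality behind the ATE survival and CAFS power in RSA 9.3 is about twice that in the primary-power simulations, and the two are not reconciled

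*SAP*

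**What the plan says.** **Primary power.** SAP Appendix 1, section 3.1, simulates the 24-week comparison of "N=165 treated on the anchor 120mg dose in Regimen F and N=135 shared controls". Its event inputs are "Mortality rate of 5% over 24 weeks" and "Non-mortality dropout rate of 2% per month". RSA 9.3 cites these simulations for its primary power statement.

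**Extension-period power.** RSA 9.3 then compares 165 participants on 120 mg throughout with 75 who start on placebo and move to 120 mg. It states about 80% power for survival to the end of the active treatment extension (ATE) and about 85% for CAFS at ATE Week 52. The control input is an "18-month survival rate of 70% for placebo RCT/120 mg ATE group", against 86% in the early-treated group. Accrual takes 12 months, total duration is at most 30 months, and alpha is two-sided 0.05. RSA 9.3 adds a "13% drop-out rate due to non-mortality reasons", with no period, and states the model: "An exponential distribution was assumed for power assessment of CAFS and survival endpoints".

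Neither section refers to the other's mortality figure or explains the difference.

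**The concern.** The 75 Regimen F placebo participants are in both calculations: alone in RSA 9.3, and among the 135 shared controls in Appendix 1. The event also appears to be the same. SAP 6.3 uses death or death equivalent in the primary model, and RSA 2.2 defines ATE overall survival in that way. A constant hazard allows the two rates to be compared at 24 weeks, when this group is still on placebo, and there they differ about twofold.

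The direction is also unexpected. Under RSA 4.4 the placebo group moves to 120 mg after Week 24, so an effective drug should lower its later mortality. Yet the 18-month survival that Appendix 1 implies for controls (84.6%) is almost what RSA 9.3 assigns to the early-treated arm (86%).

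Survival power depends on the number of deaths. If mortality follows Appendix 1, about half the deaths behind the stated 80% would occur, and a non-significant ATE survival result would say much less than a reader of RSA 9.3 would suppose.

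**Working it through.** **Inputs.** From RSA 9.3: 70% and 86% survival (both taken at 18 months), 165 vs 75, 12-month accrual, 30-month maximum (so 18 to 30 months of follow-up), 13% dropout, exponential survival, two-sided 0.05. From Appendix 1, section 3.1: 5% mortality per 24 weeks (24 weeks = 5.52 months) and 2% dropout per month.

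**1. Mortality on one scale (exponential).**
- RSA control hazard: -ln(0.70)/18 = 0.0198 per month. Mortality at 24 weeks: 1 - exp(-0.0198 × 5.52) = 10.4%.
- Appendix 1 hazard: -ln(0.95)/5.52 = 0.0093 per month. Survival at 18 months: exp(-0.0093 × 18) = 84.6%.
- Ratio: 0.0198/0.0093 = 2.1.
- RSA hazard ratio: ln(0.86)/ln(0.70) = 0.423, held fixed below.

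**2. Method.** With death hazard h and dropout hazard d, the chance of an observed death by follow-up u is h/(h+d) × [1 - exp(-(h+d)u)]. This is averaged over u from 18 to 30 months, or taken at u = 18. Each power range runs from Schoenfeld, Φ(0.861 × √(D × 0.6875 × 0.3125) - 1.96), to the version with variance 1/d0 + 1/d1, where d0 and d1 are the deaths per arm and D is their sum.

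**3. The plan's own figure.** Taking the 13% as a cut in sample size (N × 0.87), with 18 to 30 months of follow-up, gives 50.7 deaths and a Schoenfeld power of 81.1%. Taking it as 13% per year gives 51.2 deaths and 81.4%. The stated 80% reproduces.

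**4. Changing the inputs.**

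| Control mortality | Dropout | Deaths, 18-30 mo | Power | Deaths, fixed 18 mo | Power |
|---|---|---|---|---|---|
| RSA 9.3 | 13% over 18 mo | 53 | 83-88% | 43 | 74-80% |
| RSA 9.3 | 2% per month | 47 | 78-84% | 39 | 70-76% |
| Appendix 1 | 13% over 18 mo | 27 | 55-61% | 21 | 45-51% |
| Appendix 1 | 2% per month | 24 | 49-55% | 19 | 42-47% |

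Example, last row, 18-30 months: 11.9 + 11.8 = 23.7 deaths; 0.861 × √(23.7 × 0.2148) - 1.96 = -0.02, so power is 49%. Freedman and Lachin-Foulkes versions reach at most 64% in the two Appendix 1 rows. With Appendix 1 mortality and no dropout at all, 30 deaths give 59-65%. The loss therefore comes from mortality.

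**5. A hazard that fits both figures.** With 5% mortality by Week 24 and 70% survival at 18 months, the later hazard is -ln(0.70/0.95)/(18 - 5.52) = 0.0245 per month, which is 2.6 times 0.0093. With hazard ratio 0.423 and 13% dropout over 18 months, this gives 55 deaths and 84-89% (18-30 months), or 42 deaths and 74-80% (fixed 18 months). These powers are practically those of the RSA's exponential inputs.

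**6. Dropout on one scale.** 2% per month is 1 - 0.98^5.52 = 10.6% at 24 weeks and 1 - 0.98^18 = 30.5% at 18 months. The RSA's 13% is 2.5% per month if it covers 24 weeks, and 0.77% per month if it covers 18 months.

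**7. CAFS.** The documents give 20% slowing and an SD of 9.0, but no control ALSFRS-R decline. With an assumed decline of 12 to 20 points, a simulated rank test gives 83% to 96% on the RSA inputs (13% dropout) and 57% to 84% on Appendix 1 mortality and dropout. With Appendix 1 mortality and dropout kept at 13%, it gives 66% to 91%. This shows direction only.

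**The case against.** The strongest defence is that Appendix 1 covers only 24 weeks and states no hazard shape there, so carrying its 5% forward to 18 months is an extrapolation. Step 5 shows that a hazard rising after Week 24 satisfies both mortality figures and leaves the survival power near 80%. This stands as a possible explanation, but it is not the one in the plan. RSA 9.3 states an exponential model, which means a constant hazard. The rise would also have to begin when the placebo group starts active drug, although RSA 9.3 says its ATE assumptions allow for a partial cross-over effect.

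The consequence is also limited. ATE survival and CAFS at ATE Week 52 are not in the SAP 6.5.1 testing sequence, and no sample size or decision rule rests on these powers.

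A reader might infer more than the documents support:

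- **That RSA 9.3 contains an arithmetic error.** It does not. Its survival power reproduces from its own inputs.
- **That the documents plan for two different patient populations.** They hold two sets of assumptions for one regimen, with different horizons and control groups.
- **That the dropout rates contradict each other.** The 13% has no stated period. Over 24 weeks it is close to the 10.6% implied by 2% per month. With 18 to 30 months of follow-up, changing dropout alone leaves survival power at 78-84%. RSA 7.6 also plans vital-status checks for all randomized participants, so visit dropout need not mean loss to survival follow-up.
- **That a CAFS loss of known size is established.** It depends on an assumed decline.

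**Conclusion.** The mortality inputs conflict under the model RSA 9.3 states: 10.4% against 5% at 24 weeks, or 70% against 84.6% survival at 18 months. If the Appendix 1 rate holds throughout, ATE survival power is about 49-61% with 18 to 30 months of follow-up, or 42-51% with a fixed 18 months, instead of about 80%. CAFS power would fall by an amount the documents do not allow to be computed.

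This rests on a constant hazard, a hazard ratio kept at 0.42, and dropout between 13% over 18 months and 2% per month. It would be wrong to read 49-61% as the trial's true power, because nothing in the documents shows which mortality rate is right. The supportable conclusion is that a stated power rests on an input that conflicts with the primary simulations, without explanation. Correcting RSA 9.3 is worthwhile; the design itself is not in question.

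**What to change.** In RSA 9.3, do one of the following:

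1. Restate the ATE survival and CAFS powers on the Appendix 1 mortality rate, or show both rates side by side.
2. Replace the exponential assumption with a stated piecewise hazard (about 0.0093 per month to Week 24, then about 0.0245), justify the 2.6-fold rise in a group that has moved to active drug, and restate both powers. Survival power then stays near 80%.

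In either case, state the period that the 13% non-mortality dropout covers, and give the control ALSFRS-R decline used for CAFS so that its power can be checked.

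The cost is a recalculation and some wording in RSA 9.3. Under option 1 the stated power becomes less favourable. Enrolment and the primary analysis do not change.

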3.2 Operating Characteristics Primary Analysis

For each scenario and treatment effect, we simulate 10000 clinical trials. We present overall average operating characteristics across all simulated trials. All simulations do not include early futility stopping. For each simulation scenario and treatment effect, we report the following regimen-specific operating characteristics for the first regimen:

- Probability of regimen success
- · Average estimate of the treatment effect.

Table 3.2.1 shows the overall operating characteristics for Regimen F under the proposed design for the base simulation scenarios with and without futility stopping. The regimen has greater than 80% power to detect a 30% slowing of mortality and function in the

anchor dose. Under the null there is no bias and an estimated 2.5% type I error and a 11% probability of stopping early for futility.

Scenario	Power / Type I Error No Futility	Effect Estimate No Futility	Prob. Stop Early Futility	Power / Type I Error w/ Futility
Null (0% Slowing)	0.025	1.00	0.10	0.025
30% slowing of Function and Mortality	0.843	0.70	<0.001	0.843
30% slowing of Function only, 0% slowing of Mortality	0.801	0.71	<0.001	0.801

